Click on the check box (or double click and type an "X" if using Google Docs).

56 It is reasonable that researchers could discover or suspect child or elder abuse.

57 It is reasonable that researchers could learn of an incident that could require reporting under Title IX.

58 It is reasonable that researchers could discover incidental findings or other information of medical interest about a participant's previously unknown condition.

59 Articulate methods for addressing and reporting incidental findings, if applicable.

To input text, click in the light grey area below.

PRIVACY AND CONFIDENTIALITY

60 Privacy

Describe how you will protect the identity and privacy of study participants during each phase of research. Privacy focuses on the individual participants rather than data. In this section, researchers should focus on issues such as where research activities take place and how participant involvement is protected from non-participants.

Describe methods to ensure participants' privacy during identification, recruitment, screening, the consent process, the conduct of the study, and dissemination of data.

To input text, click in the light grey area below.

Surgeons (residents, fellows, and attendings performing gynecologic surgery) will be identified from the Department of Women's Health at the University of Texas at Austin Dell Medical School. Participants will be introduced to the study and interested participants will be assessed for inclusion. Written informed consent will be obtained by the PI.

Data will be collected and stored in our institution's REDcap, a secure electronic application for research.

UT Austin policies for Protected Health Information will be followed. There will not be any patient PHI data collected in this study however. There will be a spreadsheet source to de-identify the participants that will be kept on a password protected, encrypted USB drive with access only by the fellow collecting the data. All participant data will be deidentified as it is stored in REDcap. Note, the participants are not patients. The data will be kept for the required 6 years after completion of the study and then destroyed.

Confidentiality and Data Security Plan

Click on the check box (or double click and type an "X" if using Google Docs) that best describes the confidentiality and data security plan and provide additional details regarding how you will protect the confidentiality of data or address confidentiality concerns.

61 **Identifiers will be coded to protect confidentiality.**

61a **If true, state how data is coded and where identifiers are stored.**

To input text, click in the light grey area below.

UT Austin policies for Protected Health Information will be followed. There will not be any patient PHI data collected in this study, however. There will be a spreadsheet source to de-identify the participants that will be kept on a password protected, encrypted USB drive with access only by the fellow collecting the data. All participant data will be deidentified as it is stored in REDcap. Note, the participants are not patients. The data will be kept for the required 6 years after completion of the study and then destroyed.

62 **Identifiable data will be destroyed.**

62a If true, describe destruction plan and timeline

To input text, click in the light grey area below.

The data will be kept for the required 6 years after completion of the study and then destroyed.

63 Identifiable data will not be destroyed.

63a If true, provide rationale for retaining identifiable data indefinitely.

To input text, click in the light grey area below.

64 Data Access

Click on the check box (or double click and type an "X" if using Google Docs) for each group of individuals that will have access to study data.

If you plan on creating a repository, complete the repository form as well.

- | | | |
|--|--|---|
|  Study Team Members |  External Collaborators |  Data coordinating center |
|  Sponsor |  Future Sharing with other researchers | |

Others
Describe below. To input text, click in the light grey area below.

65 Describe data sharing plan for each group checked above and state whether researchers plan on sharing identifiable, coded, or de-identified data

To input text, click in the light grey area below.

Study team members will have access to deidentified data. Data will not be shared with any other institution or non-study team members.

Certificate of Confidentiality

Click on the check box (or double click and type an "X" if using Google Docs) to identify each element below that may require additional information to be disclosed in the consent form.

If a Certificate of Confidentiality is not applicable for this study, skip to 68.

66 The study requires a Certificate of Confidentiality.

67 NIH has issued a Certificate of Confidentiality for this study.

- 68 A Certificate of Confidentiality has not been obtained, but there are plans to apply for one.

COMPENSATION AND COSTS

Compensation

Click on the check box (or double click and type an "X" if using Google Docs).

- 69 Subjects receive compensation.
- 70 Subject will not receive compensation.

Skip to question 74 if subjects will not receive compensation.

71 Total Amount of Compensation

To input text, click in the light grey area below.

72 Type of Compensation

Click on the check box (or double click and type an "X" if using Google Docs) for each form of compensation that will be provided.

- | | | | | | |
|--------------------------|---------------|--------------------------|----------|--------------------------|------------|
|  | Cash |  | Check |  | Gift Card |
|  | Course Credit |  | ClinCard |  | Tango Card |
|  | Other | | | | |

Describe, To input text, click in the light grey area below.

73 Proration Schedule

To input text, click in the light grey area below.

- 74 Amount of compensation and its form is reasonable for this population for the activities requested of them.

75 Costs

Click on the check box (or double click and type an "X" if using Google Docs) each applicable item regarding costs.

- Participants will have no costs associated with this study

Standard of care procedures contributing to study data

Research procedures not associated with standard of care

Administration of drugs / devices

Study drugs or devices

Transportation and parking

76

Describe all costs below.

To input text, click in the light grey area below.

References:

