Work-related musculoskeletal disorders (MSDs) are prevalent among surgeons and include cumulative trauma disorders, repetitive strain disorders, repetitive motion disorders and overuse syndromes affecting the muscles, nerves, tendons, ligaments, cartilage, or spinal disks.^{1,2} A recent meta-analysis found that prevalence of work-related pain ranged from 35%-60% across surgical subspecialties.³ The risk of these disorders may be higher depending on the route of surgery.⁴ Gynecologists are at risk of developing work-related MSDs. One study found that 86.7% of vaginal surgeons in urogynecology reported ever having work-related MSD.¹ MSDs affect the health of individual surgeons and the stability of the surgeon workforce with up to 12% of surgeons with work-related MSD requiring a leave of absence, work restriction, or early retirement.³

Improving surgeon ergonomics and instituting intraoperative “microbreaks” and exercises may prevent work-related MSD among gynecologic surgeons. Prior studies have shown improvement in work-related discomfort or stress among surgeons with intraoperative breaks, but there are no prospective studies evaluating the impact of intraoperative exercises among gynecologic surgeons. One multi-center cohort study found that targeted stretch micro breaks diminished impact of pain on body parts, performance, and mental focus among surgeons in a variety of specialties.⁵ Another multi-center cohort study found that intraoperative exercise breaks significantly reduced discomfort with minimal impact on distractions or flow during surgery.⁶ A randomized control trial showed that intraoperative work breaks during complex laparoscopic surgeries reduced psychological stress without affecting performance or operative time.⁷

The goal of this study is to evaluate the effect of intraoperative microbreaks and exercises on gynecologic surgeon body discomfort by conducting a randomized trial. We hypothesize that gynecologic surgeons will experience decreased pain on surgery days with intraoperative microbreaks and exercises without compromising overall surgical performance.

4 Design and Methodology

Provide information regarding study design or data collection methodologies. Details regarding protocol specific research procedures will be discussed in a later section.

To input text, click in the light grey area below.

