This is a prospective randomized trial to assess the effect of intraoperative microbreaks and exercises on gynecologic surgeon body discomfort. Surgery days among gynecologic surgeons will be randomized to include or not include intraoperative microbreaks with specific exercises. Data on body part discomfort and surgeon task load will be collected on each surgery day.

[figure not shown]
5 Data Analysis

Describe the data analysis plan, including any statistical procedures or power analysis.

To input text, click in the light grey area below.

Design

Describe the design of your study –

Demographic and baseline characteristics

The baseline survey includes information such as surgeon age, gender, weight, height, dominant hand, surgical volume, years practicing surgery, and activity level.

Nordic Musculoskeletal Questionnaire

At the beginning of the study, each participant will complete a baseline questionnaire adapted from the standardized Nordic Musculoskeletal Questionnaire (NMSQ)⁸ and a survey developed by Plerhoples et al.⁹ The NMSQ is a validated questionnaire for the analysis of musculoskeletal symptoms and assesses for history of trouble (ache, pain, discomfort) in body part regions.

Primary outcome

Body Part Discomfort (BPD) scale

On each of the eligible surgery days, we will collect data on body part discomfort and surgical experience using the Body Part Discomfort (BPD) scale. The BPD scale measures body part discomfort using a 10-point scale (1 corresponds with no discomfort and 10 corresponds to maximum body discomfort) for body part regions. Body part regions include neck, shoulders, arms, wrist/hands, upper back, low back, hips/thighs, knees, ankles/feet. Body part discomfort will be summarized by the mean severity of all ratings by the subjects, known as the Body Part Discomfort Severity (BPDS) index. This summary measure will be calculated from all of the individual BPD ratings for each posture in the present study. We will compare self-reported BPDS at the beginning of the surgery day to the end of the surgery day and calculate the change by subtracting the BPDS reported at the end of day minus beginning of day. When appropriate we will control for the total number of minutes spent in surgery during the day.

Secondary Outcome:

Surgery Task Load Index (SURG-TLX)

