Similar to the BPD, we will collect data on a modified SURG-TLX on each of the eligible surgery days. The modified SURG-TLX will be evaluated at the end of each surgery day to assess participant experience throughout the surgery day. The SURG-TLX measures 6 areas: mental demands, physical demands, task complexity, situational stress, and distractions. Each of the 6 areas is rated on a scale of 0 to 100, which is added to generate a sum score. The sum score will then be compared across surgery days with and without the intervention.

Data will also be collected from medical records about each surgery in the study. The following perioperative data will be collected: surgeries performed, operative time, and intraoperative complications (i.e. bladder/bowel injury, large vessel injury, transfusion, allergic reaction, difficulty ventilating, ICU admission).

At the conclusion of the study, an anonymous exit survey will be performed to give all participants an opportunity to provide feedback. Data will be collected on the results of the exit survey. The exit survey will include questions about the participants experience performing the exercises including ease of performing exercises and incorporating into the surgical day.

Randomization

To randomize surgeons, we will first construct Williams squares where exercise follows no exercise (and vice versa) the same number of times.¹⁰ After the Williams squares are constructed and selected, individual sequences are randomly assigned to the surgeon. Sequence randomization will occur according to a predetermined computer-generated scheme prepared by a study statistician.

Statistical Analysis

Descriptive statistics (means, standard deviations, frequencies) will characterize the sample to assess comparability of the intervention and control surgery days. Chi-square test or Fisher's exact test will be used for categorical variables. Continuous variables will be examined for normality using the Shapiro-Wilk test; normally distributed continuous variables will be compared using the Student's t-test and those non-normally distributed will be compared using the Mann-Whitney U test. We will use linear mixed models to test for an association between BPDS and the targeted micro breaks/exercise intervention across surgery days. We will exclude surgeons who do not provide self-reported BPDS data on both days for a certain body part.

Power analysis:

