With feet hip width apart, bring palms together in a prayer position. Deeply inhale, then slowly squat down pushing the buttocks back, as if sitting down in a chair while slowly exhaling. Avoid letting the knees in front of the ankles, and go only as low as can be maintained with control. Keep the chest up and slight arch to the back. Then, on an exhale slowly rotate the torso to the left as far as can be comfortably done without moving the hips and continuing to breath. Return to center, then do this motion to the right. Return to center, and rise to a stand.

Forward Bend

Stand straight up, feet hip width apart. Cross arms. Engage the glutes and arch the back. With a slight bend in the knees, inhale and then on your exhale hinge forward at the hips until a stretch is felt in the hamstrings or the low back. Avoid rounding the back and avoid bringing arms close to legs. Stand up slowly keeping the glutes engaged and back straight.

Data Collection Sheet:

Baseline surgeon data:	
Age (years)	
Gender (male/female)	
Weight (lb.)	
Height (in.)	
Dominant hand (right/left)	
Years practicing surgery since residency	
Number of cases performed per year	
Number of hours exercising per week in the past month (hrs)	
Data for each surgery day:	
Surgeon BPDS score at beginning of day	
Surgeon BPDS score at end of day	
Surgeon SURG-TLX score at end of surgery day	
Data for each surgery:	
Hysterectomy performed	

Route of Surgery	
Operative time (surgery start time to surgery stop time)	
Intraoperative complications	
Exit survey:	
The intraoperative exercises helped to reduce discomfort: (strongly disagree/disagree/agree/strongly agree)	
It was easy to understand the exercises as demonstrated in the video: (strongly disagree/disagree/agree/strongly agree)	
It was easy to understand the exercises as demonstrated in the PDF document: (strongly disagree/disagree/agree/strongly agree)	
I had to modify the exercises as demonstrated in the PDF document: (strongly disagree/disagree/agree/strongly agree)	
The intraoperative exercises did NOT disrupt the workflow in the operating room: (strongly disagree/disagree/agree/strongly agree)	
I will perform the intraoperative exercises (or some modification of them) in my future practice (strongly disagree/disagree/agree/strongly agree)	
I developed a work-related musculoskeletal disorder during the course of the study: (No/yes)	

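### Route and hysterectomy are recorded for each surgery but enter no outcome model; adjusting for them is a cheap gain in precision, mainly for operative time

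*Combined protocol and SAP*

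**What the plan says.** Section 3 (Study Background), writing about musculoskeletal disorders, states: "The risk of these disorders may be higher depending on the route of surgery". The Data Collection Sheet in Section 11 lists "Hysterectomy performed" and "Route of Surgery" among the items for each surgery.

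In Section 5, the Statistical Analysis text gives the primary analysis: "We will use linear mixed models to test for an association between BPDS and the targeted micro breaks/exercise intervention across surgery days". No other term of that model is given, not even a surgeon effect. The Primary outcome text adds one covariate: "When appropriate we will control for the total number of minutes spent in surgery during the day".

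For operative data, Section 5 says only: "The following perioperative data will be collected: surgeries performed, operative time, and intraoperative complications". No model for operative time follows. The Statistical Analysis text plans descriptive statistics that "will characterize the sample to assess comparability of the intervention and control surgery days". It assigns chi-square or Fisher's exact tests to categorical variables, and the Student t or Mann-Whitney test to continuous ones.

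**The concern.** Surgery days differ in what is booked. If route or procedure influences discomfort or duration, that variation stays in the residual of every comparison between exercise and no-exercise days, although the information is already being recorded.

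The point bites hardest for operative time. The hypothesis in Section 3 includes that performance will not be compromised, and Section 40 lists longer operative time as a risk. Yet the only tests that could apply have no surgeon term and no case-mix term. A few added minutes would be sought against the whole spread of procedures and surgeons. An inconclusive result is then likely, and could be misread as showing no effect on duration.

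For discomfort, the one named covariate is a weak substitute for route. It is conditional and does not carry posture or approach. It is also observed after assignment, and Section 11 says the breaks may add time to the surgery.

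**Working it through.** **1. Where the recorded case-mix items are used.** Route and hysterectomy are recorded per surgery (Section 11). They appear in no outcome model, stratification or subgroup in Section 5. The Randomization text assigns each surgeon a sequence of day types and does not mention route. The comparability check could include both items, but it describes imbalance and does not adjust for it.

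**2. The plan's own power figure.** Inputs from Section 5: f = 0.25, alpha = 0.05, m = 10 measurements. Assumed, because not stated: correlation rho = 0.5 and sphericity. The noncentral F test has lambda = f² × N × m / (1 − rho), with m − 1 and (N − 1)(m − 1) degrees of freedom.
- N = 15: lambda = 0.0625 × 15 × 10 / 0.5 = 18.75, power 0.85.
- N = 20: lambda = 25, power 0.95.

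Both agree with Table 1. (The text pairs power 0.85 with 20 surgeons; that is a separate matter.) Replacing f by f / √(1 − R²) at N = 20 gives 0.96, 0.97 and 0.99 for R² = 0.05, 0.10 and 0.20. On the plan's own basis there is little to gain for BPDS.

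**3. Effect on interval width.** Let R² be the share of within-surgeon variance explained by route and procedure beyond the other model terms. The documents give no value, so every R² here is an assumption. Width ratio = √(1 − R²); equivalent extra days = 1/(1 − R²) − 1.

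| R² | Width ratio | Narrower by | Equivalent extra days |
|---|---|---|---|
| 0.05 | 0.975 | 2.5% | 5% |
| 0.10 | 0.949 | 5% | 11% |
| 0.20 | 0.894 | 11% | 25% |
| 0.30 | 0.837 | 16% | 43% |
| 0.40 | 0.775 | 23% | 67% |

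The first three rows are the range assumed for BPDS change, and the last two the range assumed for operative time.

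**4. BPDS power for the two-condition contrast.** Reading Section 14 as 10 + 10 days per surgeon, 20 surgeons give 200 v 200 days. In within-surgeon SD units, SE = √(2/200) = 0.10.
- At d = 0.5 (f = 0.25 for two conditions, d = 2f), power exceeds 0.99 with or without adjustment.
- At d = 0.25, inside the range of 0.00 to 0.48 that Section 5 cites, power is 0.70 unadjusted. It is 0.73, 0.75 and 0.80 at R² = 0.05, 0.10 and 0.20.

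This assumes the effect does not vary between surgeons.

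**5. Operative time: signal against error.** Section 11 places one break before time-out, one at 45 to 75 minutes and one at the end of the case, each about 1.5 to 2 minutes. Between surgery start and stop there are thus one or two breaks: 1.5 minutes up to 2 × 2 = 4 minutes. On an illustrative 120-minute case that is 1.5/120 = 1.3% to 4/120 = 3.3%. The documents give no SD for operative time, so whether such an increase is detectable cannot be computed.

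The missing surgeon term adds its own cost. If surgeons contribute equally to both day types, the SE of the pooled test relative to a within-surgeon one is 1/√(1 − ICC). That is 1.05, 1.12, 1.20 and 1.41 for an assumed ICC of 0.1, 0.2, 0.3 and 0.5.

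**6. Chance imbalance.** If one route made up half of the days (an assumption), the difference in its share between day types has SD √(0.25 × 2/200) = 0.05. Imbalances of up to about 10 percentage points (1.96 × 0.05 = 0.098) would be unremarkable.

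**The case against.** The case for leaving the plan alone is substantial for the primary outcome. Days are randomised, each surgeon contributes both day types, and the outcome is a within-day change. If the mixed model has a surgeon effect, differences between surgeons in usual route drop out, and for a surgeon who always uses one route the gain is near zero. Minutes in surgery may already carry part of the case mix. The width ratio is a best case: variation in the exercise effect between surgeons is not reduced, and one route per day discards the rest of a multi-case day. All of this stands, and it is why the BPDS gain is probably small.

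Four stronger readings are tempting but unsupported:
- A reader might infer that route and procedure enter no comparison at all. The planned comparability check of surgery days is worded broadly enough to cover both.
- A reader might infer that the plan treats route as an established cause of the discomfort it measures. The background sentence is hedged and concerns disorders; nothing links route to same-day BPDS change.
- A reader might infer that discomfort is analysed with no covariate. Minutes in surgery is named, conditionally.
- A reader might infer that operative time is the plan's main measure of performance. It is listed as perioperative data; the named secondary outcome is SURG-TLX.

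The objection does not answer the operative-time point: no stated analysis has a surgeon, route or procedure term.

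**Conclusion.** The point holds as a cheap improvement, chiefly for operative time. No outcome model uses route or hysterectomy, and operative time falls to unadjusted tests. A reader might infer that the treatment estimate is biased by case mix. Randomisation of days rules that out in expectation; what remains is lost precision and chance imbalance.

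The size rests wholly on assumed R² values: at most 2.5% to 11% narrower for BPDS change (R² 0.05 to 0.20) and at most 16% to 23% narrower for operative time (R² 0.30 to 0.40). At the plan's own effect size the adjustment would not change the BPDS conclusion; it could matter for smaller effects within the cited range.

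**What to change.** 1. Analyse operative time per surgery on the log scale in a mixed model with a surgeon effect and with route and hysterectomy (yes/no) as fixed factors. Several surgeries on one day share one assignment, so a random effect for day within surgeon is also needed. Report the confidence interval for the intervention effect, so that the reader sees which increases are excluded, rather than only a non-significant test.
2. State the surgeon effect in the BPDS-change mixed model and pre-specify route as a day-level fixed factor. Take the booked route of the day's longest booked case from the schedule as it stood when the assignment was released. Conversions then do not enter as post-assignment information, and multi-case days have a rule. Pool rare routes by a stated rule.

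Cost: analysis-plan wording, one schedule field per case (the data sheet holds route and hysterectomy per surgery but no booked route), and a few model degrees of freedom.

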- Include time commitment of participants

To input text, click in the light grey area below.

Potential participants include residents, fellows, and attendings performing gynecologic surgery (including benign gynecologists, gynecologic oncologists, minimally invasive gynecologists, and urogynecologists). We will recruit surgeons from the Department of

Women's Health at the University of Texas at Austin Dell Medical School. Surgeons will need to have operated on average at least 2 days per month over the last 12 months. Written informed consent will be obtained. Eligible surgery days must include at least one surgery with total operative time of at least 2 hours. Surgeons will be excluded if they are unable to perform the exercises.

Upon agreement to participate in the study, surgeons will complete baseline questionnaires adapted from the standardized Nordic Musculoskeletal Questionnaire (NMSQ)⁸ and a survey developed by Plerhoples et al.⁹ The NMSQ is a validated questionnaire for the analysis of musculoskeletal symptoms and assesses for history of trouble (ache, pain, discomfort) in body part regions. The survey includes information such as surgeon age, gender, weight, height, dominant hand, surgical volume, years practicing surgery, and activity level.

Once participants are enrolled, all participant surgery days will be assessed for inclusion based on the inclusion criteria above. Surgery days will be randomized to surgery days with microbreaks and exercises and surgery days without microbreaks and exercises. The surgeon will be informed of the randomization assignment prior to the surgery day.

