Surgery days randomized to intraoperative microbreaks and exercises will include standardized breaks lasting approximately 1.5-2 minutes. During these breaks, surgeons will perform a set of targeted stretches or exercises while remaining sterile. These exercises were developed with the assistance of a physician specialized in Physical Medicine and Rehab. The exercises will be performed just before surgical time-out, at a surgically safe and convenient time 45-75 mins after the start of the case and at the end of the case. A surgically safe and convenient time means the surgeon feels that it is safe to take an approximately 1.5-2 minute break during the procedure at that time. Surgeons will skip the microbreak if there is no surgically convenient or safe time during the case. Surgeons will stop the microbreak at any point if needed to ensure patient safety. The microbreaks performed during the surgery may add time to the surgery in approximately 1.5-2 minute increments, however prior studies have shown no difference in operative time with addition of microbreaks. Attached is a document outlining the exercises including photos with exercise cues and a video demonstrating the exercises. Participants will have access to these documents before and during the study.

On each surgery day, participating surgeons will complete the "Surgery Day Questionnaire" which will include the Body Part Discomfort (BPD) scale and Surgery Task Load Index (SURG-TLX). The Corlett and Bishop BPD Scale was originally created in 1976 and is a validated technique to assess work-related discomfort by body part regions.^{11,12}

Another measure of work-related stress during surgery is the SURG-TLX. This is a validated tool based off the NASA-TLX used to assess overall workload including mental demands, physical demands, temporal demands, task complexity, situational stress, and distractions.¹³ At the beginning of all surgery days, the participating surgeon will complete a baseline BPD scale as the first part of the “Surgery Day Questionnaire”. Following each surgery day, the surgeon will complete both the BPD scale and the SURG-TLX survey to complete the “Surgery Day Questionnaire” for that day. Participating surgeons are asked to inform the research team if they develop any new work-related injury during the study period.

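### The primary model names no beginning-of-day BPDS covariate, although the rating is collected every surgery day; adding it could sharpen the estimate, and the rule for surgery minutes should be fixed in the same edit

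*Combined protocol and SAP*

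**What the plan says.** Section 5 (Data Analysis), under Primary outcome, defines the daily outcome: the team will "calculate the change by subtracting the BPDS reported at the end of day minus beginning of day". It then adds: "When appropriate we will control for the total number of minutes spent in surgery during the day". No criterion for this is given, and no time for deciding it.

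Under Statistical Analysis, the only sentence on the model is: "We will use linear mixed models to test for an association between BPDS and the targeted micro breaks/exercise intervention across surgery days". It does not say whether the dependent variable is the change or the end-of-day score, and it names no covariate and no random effect. The same paragraph plans descriptive statistics "to assess comparability of the intervention and control surgery days".

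Section 11 (Procedure Description) shows that the baseline exists for each day: "At the beginning of all surgery days, the participating surgeon will complete a baseline BPD scale". The Data Collection Sheet has a matching line, "Surgeon BPDS score at beginning of day". Two other statements in Section 11 bear on the point. On disclosure: "The surgeon will be informed of the randomization assignment prior to the surgery day". On operating time: "The microbreaks performed during the surgery may add time to the surgery in approximately 1.5-2 minute increments".

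**The concern.** A change score analysed without a baseline term fixes the slope of the evening rating on the morning rating at 1. If the true within-surgeon slope is different, the part of the morning rating that was over- or under-subtracted stays in the residual and widens the confidence interval. Estimating the slope removes it. The morning rating is already collected, so the price in data is nil.

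Precision is worth having here. For 20 surgeons, Table 1 in Section 5 gives power 0.95 at f = 0.25, but 0.79 at f = 0.20 and 0.49 at f = 0.15.

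The condition attached to surgery minutes is a related gap. It allows two versions of the primary analysis, and the plan does not say which one counts. Minutes are also observed after assignment, and the protocol itself says that the breaks may lengthen surgery. Whether minutes belong in the model at all is therefore a decision of substance.

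**Working it through.** **Inputs.** From the documents: 20 surgeons, each with 10 intervention days and 10 control days (Sections 5 and 14). The plan gives no SD of BPDS, no morning-evening correlation and no figure for the gain from adjustment, so there is no figure of its own to reproduce on this point. Assumed: within-surgeon morning-evening correlation r; morning/evening SD ratio k; evening SD set to 1; a random surgeon intercept; and, at first, no variation of the effect between surgeons.

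**1. Precision.** The day-level residual variance is 1 + k² − 2rk for the change score and 1 − r² after adjustment. The variance ratio, adjusted to change, is (1 − r²)/(1 + k² − 2rk), and the interval narrows by 1 − √ratio.

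| k | r = 0.3 | r = 0.5 | r = 0.7 |
|---|---|---|---|
| 1 | 0.91/1.40 = 0.65 (19.4%) | 0.75/1.00 = 0.75 (13.4%) | 0.51/0.60 = 0.85 (7.8%) |
| 0.7 | 0.91/1.07 = 0.85 (7.8%) | 0.75/0.79 = 0.95 (2.6%) | 0.51/0.51 = 1.00 (0%) |
| 0.5 | 0.91/0.95 = 0.96 (2.1%) | 0.75/0.75 = 1.00 (0%) | 0.51/0.55 = 0.93 (3.7%) |

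The gain is nil where the true slope r/k equals 1. A simulation of the 20 × 20 layout (20,000 runs) gave 0.656/0.758/0.861, 0.847/0.951/1.003 and 0.957/1.003/0.924 for the three rows, in agreement with the formula.

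**2. Outside the grid.** At r = 0 and k = 1 the ratio is 1/2 and the narrowing 29.3%.

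**3. Effect varying between surgeons.** Take the most favourable cell, r = 0.3 and k = 1. With 10 + 10 days, the variance of one surgeon's estimate is 1.40 × (1/10 + 1/10) = 0.28 for the change score and 0.91 × 0.2 = 0.182 after adjustment. An assumed between-surgeon effect SD of 0.3 evening SD adds 0.09 to both: 0.272/0.370 = 0.735, or 14% narrower. An SD of 0.5 adds 0.25: 0.432/0.530 = 0.815, or 10% narrower.

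**4. Choice of dependent variable.** Once the baseline terms are in the model, the intervention estimate does not depend on this choice. In three simulated data sets it was −0.15419, −0.08437 and −0.25233 for both the end-of-day and the change outcome. If the plan means end-of-day BPDS with no baseline, the narrowing from adjustment is 1 − √(1 − r²), which is 4.6%, 13.4% and 28.6% at r = 0.3, 0.5 and 0.7.

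**5. Disclosure before the morning rating.** Suppose that knowing the assignment moves the morning rating by an assumed d = 0.2 evening SD. In the grid, r/k runs from 0.3 to 1.4.
- If the evening rating does not move, the change score is off by d = 0.20 and the adjusted estimate by (r/k)d, which is 0.06 to 0.28.
- If the evening rating moves equally, the change score is off by 0 and the adjusted estimate by (1 − r/k)d, which is at most 0.14 in size.

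**6. Surgery minutes, worst case.** Let ρ be the within-surgeon correlation of minutes with the outcome (assumed). Under the null, the test statistics with and without minutes are close to bivariate normal with correlation √(1 − ρ²). If the smaller p-value is always taken, type I error is 5.9%, 6.4%, 7.3% and 8.3% at ρ = 0.2, 0.3, 0.5 and 0.7. In simulation, each model used alone stayed at 4.8% to 5.1%.

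**The case against.** The strongest reply is that the plan states a valid estimator clearly and nothing in the documents contradicts it. An efficiency gain that may be zero is then a matter of preference. On validity this stands: a reader might infer that the change score is a mistake, or biased by design, and the documents do not support that.

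A second reply is that the recommended analysis uses a rating made after the assignment is known, so it could exchange an uncertain gain for a larger bias. Part of this stands. Step 5 shows that neither analysis is always safer, so only the data come free of cost. It does not defeat adjustment, because the change score depends on the same morning rating and would be reported alongside.

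A third is that one sentence about a model does not exclude a baseline term, and that BPDS there need not mean the change. That is fair. It is a reason to write the model out, and the proposed model gives the same intervention estimate under either reading of the outcome.

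Lastly, planned descriptive statistics could already cover morning BPDS by assignment. They could, but the plan does not name it.

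**Conclusion.** The point holds as a precision improvement that needs no new data, together with a missing rule for surgery minutes. The size is 0% to 19% on the width of the confidence interval, for assumed r of 0.3 to 0.7, k of 0.5 to 1 and an effect that is the same for all surgeons. It reaches 29% at r = 0 and k = 1. The 19% falls to about 14% or 10% if the effect varies between surgeons with an assumed SD of 0.3 or 0.5 evening SD.

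Two stronger readings should be avoided. A reader might turn the gain into a number of extra surgeons. The documents give no correlation, SD or effect variation to support such a figure, and the most favourable cell would dominate it. A reader might also infer that the trial's type I error is above 5%. The 5.9% to 8.3% applies only if the smaller p-value is always chosen, and nothing in the documents says that it will be. What they do show is that the choice is open.

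**What to change.** Write out one primary mixed model: intervention and beginning-of-day BPDS as fixed effects, the latter split into the surgeon's mean and the daily deviation from it, with a random surgeon intercept. Name the dependent variable; change or end-of-day will do. Report the unadjusted change score as a sensitivity analysis, and add morning BPDS by assignment to the planned comparability table. Whether period or carryover terms follow from the Williams-square randomization is a separate decision, which the same text should state.

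Replace the open condition on surgery minutes with a statement, made before the data are seen, that they are in or out of the primary model, with the other version as a sensitivity analysis.

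The cost is SAP wording, one table row and one or two estimated slopes. Each minutes rule has a price. Leaving minutes out gives up a variance reduction of ρ², which is 4%, 9% or 25% at assumed correlations of 0.2, 0.3 or 0.5. Keeping them in risks adjusting away part of an effect of the breaks. With an assumed 1.5 to 6 added minutes and 0.2 to 0.6 BPDS points per hour, the bias is 0.2 × 1.5/60 = 0.005 to 0.6 × 6/60 = 0.06 points. A day with several cases could exceed 6 minutes, and the break before time-out may not count in start-to-stop time.
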